7.8.2 Laboratory data

The analyses of laboratory data will be descriptive in nature and will be based on BI standard "Display and Analysis of Laboratory Data" ([10](#)). Alpha-1 Acid Glycoprotein values will only be listed.

Analyses will be based on normalised values, which means transforming to a standard unit and a standard reference range.

Descriptive statistics of laboratory values over time and for the difference from baseline (see [Section 6.7](#)) will be provided. Frequency tables of changes between baseline and last value on treatment with respect to the reference range will be presented.

Unscheduled measurements of laboratory data will be assumed to be repeat measurements of the most recent scheduled measurement (e.g. for follow-up or confirmation of a particular value). Therefore, unscheduled measurements will be assigned to the planned time point of the previous scheduled measurement. Descriptive statistics will be calculated by planned time point based on the worst value of the subject at that planned time point (or assigned to that planned time point).

Possibly clinically significant abnormal laboratory values are only those identified either in the Investigator's comments on the eCRF or at the RPM/DBLM at the latest. It is the Investigator's responsibility to decide whether a lab value is clinically significant abnormal or not. Standard or project-specific rules for flagging clinically significant values will not be applied in this study.

Clinically relevant findings in laboratory data will be reported as AEs and will be analysed as part of AE analysis.

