4.1.4 Drug assignment and administration of doses for each subject

In the morning of Day 1, following an overnight fast of at least 10 h, all subjects will receive one single dose of the trial drug (BI 730357 BS (C-14) oral solution 5 mg/mL (10 mL; 3.7 MBq)).

The medication will be administered as a single oral dose together with 240 mL of water to a subject in the sitting position under supervision of the investigator or an authorised designee. After administration, will determine for each volunteer the residual amount of [¹⁴C]-radioactivity in the syringe used for administration. The amount of administered radiolabelled medication will be calculated based on pre- and post-dose weight of the syringe used for oral administration.

The so-called four-eye principle (two-person rule) should be applied for administration of trial medication.

During the first 4 h after drug administration, subjects are not allowed to lie down (i.e., no declination of the upper body of more than 45 degrees from upright posture) except for medical examination or if necessary for any medical reasons (e.g. adverse events). For restrictions with regard to diet and fluid intake see [Section 4.2.2.2](#).

After drug administration subjects will be kept under close medical surveillance until planned discharge from the unit on Day 15. In case release criteria for radioactivity recovery have not been met on Day 15, subjects will come back to the unit for up to five once-weekly 24 h sampling periods until discharge criteria are met or after the last collection interval Day 49-50 was completed (see [Section 3.1](#)).

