Substrates	Glucose (Serum) Creatinine Bilirubin, Total Bilirubin, Direct Protein, Total Albumin Alpha glycoprotein acid C-Reactive Protein (Quant) Uric Acid Urea Cholesterol, total Triglyceride	X X X X X X X X X X X X X X X	-- -- -- -- -- -- -- -- -- -- -- -- -- -- --	X X X X X X X X X X X X X X	X X X X X X X X X X X X X X
Electrolytes	Sodium Potassium Magnesium Calcium	X X X X	-- -- -- --	X X X X	X X X X

Proprietary confidential information © 2018 Boehringer Ingelheim International GmbH or one or more of its affiliated companies

Table 5.2.3: 1 Routine laboratory tests (cont.)

Functional lab group	BI test name [comment/abbreviation]	A	B	C	D
Urinalysis (Stix)	Urine Nitrite (qual) Urine Protein (qual) Urine Glucose (qual) Urine Ketone (qual) Urobilinogen (qual) Urine Bilirubin (qual) Urine RBC/Erythrocytes (qual) Urine WBC/Leucocytes (qual) Urine pH	X X X X X X X X	-- -- -- -- -- -- -- --	-- -- -- -- -- -- -- --	X X X X X X X X
Urine sediment (microscopic examination if erythrocytes, leukocytes nitrite or protein are abnormal in urine)	Only positive findings will be reported (for instance, the presence of sediment bacteria, casts in sediment, squamous epithelial cells, erythrocytes, leukocytes)				

A: Parameters to be determined at Visit 1 (screening examination) and at Visit 2 on Day -1

B: Parameters to be determined at Visit 2 on Day 1 (at PTM 2:00, 4:00, 12:00) and Day 2 (at PTM 24:00)

C: Parameters to be determined at Visit 2 on Days 1 (PTM -2:00), 8, 15 and 35 (for time points refer to [Flow Chart](#))

D: Parameters to be determined at Visit 3 (end-of-trial examination)

The tests listed in [Table 5.2.3: 2](#) are exclusionary laboratory tests which may be repeated as required. The results will not be entered in the CRF/database and will not be reported in the CTR. Except for drug screening, it is planned to perform these tests during screening only. Drug screening will be performed at screening and on Day -1 of the treatment period.

To encourage compliance with alcoholic restrictions, an alcohol test in urine will be performed at screening and on Day -1 of the treatment period, and may be repeated at any time during the study at the discretion of the Investigator or designee. The results will not be included in the CTR.

Proprietary confidential information © 2018 Boehringer Ingelheim International GmbH or one or more of its affiliated companies

Table 5.2.3: 2 Exclusionary laboratory tests

Functional lab group	Test name

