7.3.3 Safety analyses

Safety will be assessed for the endpoints listed in [Section 5.2.1](#). All treated subjects (that is, all subjects who received at least one dose of study drug), will be included in the safety analysis. Safety analyses will be descriptive in nature and will be based on BI standards. No hypothesis testing is planned.

The analyses will be done by 'treatment at onset'.

Proprietary confidential information © 2018 Boehringer Ingelheim International GmbH or one or more of its affiliated companies

Tabulations of frequencies/proportions will be used for the evaluation of categorical (qualitative) data, and tabulations of descriptive statistics will be used to analyse continuous (quantitative) data.

Measurements (such as ECG, vital signs, or laboratory parameters) or AEs will be assigned to the treatment (see [Section 4.1](#)) based on the actual treatment at the planned time of the measurement or on the recorded time of AE onset (concept of treatment emergent AEs).

Therefore, measurements planned or AEs recorded prior to first intake of trial medication will be assigned to 'screening', those between first trial medication intake until end of the residual effect period (see [Section 1.2](#)) will be assigned to the treatment period. Events after the residual effect period but prior to end-of-trial examination will be summarized as 'follow-up'. These assignments including the corresponding time intervals will be defined in detail in the TSAP.

Adverse events will be coded using the Medical Dictionary for Regulatory Activities (MedDRA). Frequency, severity and causal relationship of AEs will be tabulated by treatment, system organ class and preferred term. SAEs, AESIs (see [Section 5.2.2.1](#)) and other significant AEs (according to ICH E3) will be listed separately.

Laboratory data will be compared to their reference ranges. Values outside the reference range as well as values defined as clinically relevant will be highlighted in the listings. Additionally, differences from baseline will be evaluated.

Vital signs or other safety-relevant data observed at screening, baseline, during the course of the trial and at the end-of-trial evaluation will be assessed with regard to possible changes compared to findings before start of treatment.

Relevant ECG findings as judged by the investigator will be reported as AEs.

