6. GENERAL ANALYSIS DEFINITIONS

6.1 TREATMENT

For basic study information on treatments to be administered, assignments of dose groups, and selection of doses, cf. Section 4 of the CTP.

All subjects were planned to be treated with a single dose of 50 mg BI 730357 BS (C-14) (BI 730357 mixed with [C-14]BI 730357 BS)

For statistical analysis of AEs, safety laboratory data and vital signs, the following analysis phases are defined for each subject:

Table 6.1: 1 Flow chart of analysis phases for statistical analyses of AEs, safety laboratory data and vital signs

Study analysis phase	Label	Start (inclusive)	End (exclusive)
Screening	Screening	Date of informed consent	Date/time of administration of study drug
On-treatment	BI 730357	Date/time of administration of study drug	12:00 a.m. on day after end of REP (REP ends 7 days after date of administration of study drug)
Follow-up	F/U	12:00 a.m. on day after end of REP	12:00 a.m. on day after trial completion date

CTR Section 15, Appendix 16.1.13.1.8.2 and Appendix 16.1.13.1.8.3 AE displays will present results for the on-treatment phase only. Appendix 16.1.13.1.8.1 will present results for the screening, on-treatment and follow-up phase.

Additionally, the following total will be provided in CTR Section 16.1.13.1.8.1 AE tables:

- "**Total**", defined as the total over all study phases (incl. screening, on-treatment, and follow-up)

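### The laboratory shift tables close at Day 8, so scheduled values from Day 15 onward stay out of them and urinalysis has nothing to tabulate

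*SAP*

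**What the plan says.** SAP 7.8.2 plans three things for laboratory data: descriptive statistics over time, descriptive statistics for the difference from baseline, and shift tables. The shift rule reads: "Frequency tables of changes between baseline and last value on treatment with respect to the reference range will be presented".

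The SAP defines what on treatment means. Section 6.1 introduces Table 6.1: 1 with: "For statistical analysis of AEs, safety laboratory data and vital signs, the following analysis phases are defined for each subject". The table ends the on-treatment phase (exclusive) at "12:00 a.m. on day after end of REP (REP ends 7 days after date of administration of study drug"). Protocol 7.3.3 assigns measurements, laboratory parameters included, in the same way: "those between first trial medication intake until end of the residual effect period (see [Section 1.2](#)) will be assigned to the treatment period".

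The sampling schedule is in the footnotes to Protocol Table 5.2.3: 1:
- Set A is pre-dose (screening and Day -1).
- Set B is at 2, 4, 12 and 24 h and, as far as the table can be read, covers haematocrit only.
- Set C is given as: "C: Parameters to be determined at Visit 2 on Days 1 (PTM -2:00), 8, 15 and 35".
- Set D belongs to the end-of-trial examination, which the Flow Chart places between Day 16 and Day 50.

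The urinalysis (Stix) row is marked for sets A and D and not for B or C.

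**The concern.** A shift table shows how many subjects moved from inside to outside the reference range. Here it looks only at the first week after the dose, although the protocol schedules further panels for up to seven weeks. A value that is normal on Day 8 and abnormal on Day 15 or at end of trial would count as no shift.

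Urinalysis is the clearest case. Its only scheduled post-dose assessment lies in follow-up, so the table as specified has no post-dose entry. Most Stix results are qualitative, so means and standard deviations by time point are a poor substitute, and SAP 7.8.2 specifies no other frequency table for laboratory data.

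The AE tables do not fully fill this gap. SAP 6.1 limits the AE displays in Section 15 of the trial report to the on-treatment phase and shows follow-up events by phase only in Appendix 16.1.13.1.8.1. A late laboratory abnormality can therefore be missing from both the shift table and the main AE tables.

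**Working it through.** **Inputs**
- Dosing: Day 1 (Protocol 4.1.4), at about 08:00 (Flow Chart).
- REP: 7 days after the dosing date (SAP Table 6.1: 1).
- Phase end, exclusive: 00:00 on the day after the REP ends (same table).
- Laboratory times: Flow Chart and the footnotes to Protocol Table 5.2.3: 1.
- End-of-trial examination: 1 to 7 days after last discharge (Flow Chart, footnote 10). The earliest planned discharge is Day 15, so Day 16 is the earliest for a completer.

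**Phase end**
- REP end = Day 1 + 7 days = Day 8.
- Phase end = 00:00 on Day 9 = 8 × 24 h − 8 h = 184 h after dosing.
- A value is on treatment if 0 ≤ t < 184 h.

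**Post-dose schedule against that limit**

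| Time point | Hours after dose | Set | Phase |
|---|---|---|---|
| Days 1 and 2 | 2, 4, 12, 24 | B | On treatment |
| Day 8 | 168 | C | On treatment |
| Day 15 | 336 | C | Follow-up |
| Day 35, if attended | 34 × 24 + 5 = 821 | C | Follow-up |
| End of trial, earliest (Day 16, 00:00) | 15 × 24 − 8 = 352 | D | Follow-up |
| End of trial on Day 50 (13:00) | 49 × 24 + 5 = 1181 | D | Follow-up |

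For parameters in set C, the last scheduled on-treatment value is Day 8. Day 15, Day 35 and end of trial all fall outside.

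**Urinalysis.** Sets A and D only. Set A is pre-dose and set D is at 352 h or later, so there are 0 scheduled on-treatment values for any of the nine Stix tests named. An unscheduled urinalysis by Day 8 would not clearly help, because SAP 7.8.2 assigns unscheduled results to the preceding scheduled time point. For urinalysis that point is pre-dose.

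**Sensitivity to the REP.** With 6 days the phase would end at 160 h and Day 8 would drop out as well. With 8 days it would end at 208 h and nothing would be gained. Under the same day count, the window would have to run at least 14 days to reach Day 15, 15 days for Day 16, 34 days for Day 35 and 49 days for Day 50. The result does not depend on how the day boundary is read.

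**Other parameters.** TSH is in set A only and has no scheduled post-dose value. Some enzymes appear to be outside set C, but the table is broken in the copy reviewed and they cannot be identified with certainty.

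**The case against.** The strongest reply is that little depends on this table. Protocol 7.3.3 has out-of-range values highlighted in the listings, and SAP 7 lists every subject's individual values. With 6 to 8 subjects, each abnormal late result can be found by eye. The by-time-point statistics in SAP 7.8.2 are not limited to the on-treatment phase and use the worst value at each time point. Hepatic injury is an AESI reported within 24 hours, and clinically relevant laboratory findings become AEs. All of this stands. A reader might infer that abnormalities after the first week go unseen, or that the shift table is the plan's only comparison with the reference range. The documents do not support either inference.

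A second reply is that the restriction follows the protocol's own phase rule. This also stands. A reader might conclude that 7 days is too short, but the documents give no basis for that. The REP rationale is in a protocol section whose text is not available. The only human half-life visible is the roughly 28 h assumed in Appendix 10.1, and 168 / 28 = 6 half-lives. The difficulty lies in applying the phase to this table without further provision, not in the length of the phase.

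A third reply is that any last-value shift uses one value per subject. Switching to the last post-dose value would drop Day 8 and mix visits from Day 16 to Day 50. That is a sound argument against replacing the rule, but not against adding to it.

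Finally, the sponsor's laboratory display standard (SAP reference 10) was not available and may leave out parameters with no on-treatment value. If so, the SAP should say it, and urinalysis would still have no frequency summary in SAP 7.8.2.

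**Conclusion.** The point holds as a gap in the specified summary. For subjects who follow the planned schedule, the shift tables take nothing after Day 8. Of up to four post-dose sampling occasions from Day 8 onward (Day 8, Day 15, Day 35 if attended, end of trial), three lie outside the window, and urinalysis has none inside it.

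This rests on three assumptions: Table 6.1: 1 governs the wording of SAP 7.8.2, the urinalysis row is marked as it can be read, and subjects complete as planned. It is not absolute for every subject. Someone who discontinues early has an end-of-trial examination if possible, perhaps by Day 8, and could then supply an on-treatment urinalysis value. Day 35 applies only where the release criteria have not been met earlier.

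No primary or secondary endpoint is affected and no data are lost. The change is worth making because it is cheap and because the SAP does not say that leaving later values out of the table is intended.

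**What to change.** In SAP 7.8.2, keep the shift from baseline to the last on-treatment value and add two shifts against the reference range:
1. baseline to the worst post-baseline value over all post-dose visits, with worst defined as in the by-time-point tables that already use it;
2. baseline to the end-of-trial value.

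State that parameters without an on-treatment value, such as urinalysis, appear only in the added shifts. For urinalysis on the planned schedule the two will coincide. Note that a parameter with no post-dose sampling (TSH) has no shift table. Leave the AE phases in Table 6.1: 1 unchanged.

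The cost is a few extra columns from data already collected, and a footnote that they include values after the REP and so do not match the AE on-treatment phase.

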In accordance with the European Medicines Agency initiative on Important Medical Events, Boehringer Ingelheim has set up a list of further AEs, which, by their nature, can always be considered to be ‘serious’ even though they may not have met the criteria of an SAE as defined above.

The latest list of ‘Always Serious AEs’ can be found in the eDC system, an electronic data capture system which allows the entry of trial data at the trial site. These events should always be reported as SAEs as described above.

Adverse events of special interest

The term adverse events of special interest (AESI) relates to any specific AE that has been identified at the project level as being of particular concern for prospective safety monitoring and safety assessment within this trial, e.g. the potential for AEs based on knowledge from other compounds in the same class. AESIs need to be reported to the sponsor’s Pharmacovigilance Department within the same timeframe that applies to SAEs, please see [Section 5.2.2.2](#).

Proprietary confidential information © 2018 Boehringer Ingelheim International GmbH or one or more of its affiliated companies

The following are considered as AESIs:

- Hepatic injury

A hepatic injury is defined by the following alterations of hepatic laboratory parameters:

- an elevation of AST (aspartate transaminase) and/or ALT (alanine transaminase) ≥ 3 -fold ULN combined with an elevation of total bilirubin ≥ 2 -fold ULN measured in the same blood sample, or
- aminotransferase (ALT, and/or AST) elevations ≥ 10 fold ULN

These lab findings constitute a hepatic injury alert and the subjects showing these lab abnormalities need to be followed up according to the 'DILI checklist' provided in the ISF. In case of clinical symptoms of hepatic injury (icterus, unexplained encephalopathy, unexplained coagulopathy, right upper quadrant abdominal pain, etc.) without lab results (ALT, AST, total bilirubin) available, the Investigator should make sure that these parameters are analysed, if necessary in an unscheduled blood test. Should the results meet the criteria of hepatic injury alert, the procedures described in the DILI checklist should be followed.

- Severe infections (according to RCTC grading)

- Opportunistic and mycobacterium tuberculosis infections

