5.2.3 Assessment of safety laboratory parameters

For the assessment of laboratory parameters, blood and urine samples will be collected by the trial site at the time points indicated in the [Flow Chart](#) after the subjects have fasted for at least 4 h (at admission on Day -1 only) or at least 10 h (all other time points). Subjects do not need to have fasted for drug screening and for infectious serology at the discretion of the investigator or designee. Overnight fasting is not required at the discretion of the investigator or designee for retests.

The parameters that will be determined are listed in [Tables 5.2.3: 1](#) and [5.2.3: 2](#). Reference ranges will be provided in the ISF, Section 10.

Manual differential white blood cell count or urine sediment examinations will only be performed if there is an abnormality in the automatic blood cell count or in the urinalysis, respectively.

Table 5.2.3: 1 Routine laboratory tests

Functional lab group	BI test name [comment/abbreviation]	A	B	C	D
Haematology	Haematocrit Haemoglobin Red Blood Cell Count/Erythrocytes Reticulocytes, absol. White Blood Cells/Leucocytes Platelet Count/Thrombocytes (quant)	X X X X X X	X -- -- -- -- --	X X X X X X	X X X X X X
Automatic WBC differential, relative	Neutrophils/Leukocytes; Eosinophils/Leukocytes; Basophils/Leukocytes; Monocytes/Leukocytes; Lymphocytes/Leukocytes	X	--	X	X
Automatic WBC differential, absolute	Neutrophil, absol.; Eosinophils, absol.; Basophils, absol.; Monocytes, absol.; Lymphocytes, absol.	X	--	X	X
Manual differential WBC (if automatic differential WBC is abnormal)	Neut. Poly (segs); Neut. Poly (segs), absol.; Neutrophils Bands; Neutrophils Bands, absol.; Eosinophils/Leukocytes; Eosinophils, absol.; Basophils/ Leukocytes; Basophils, absol.; Monocytes/ Leukocytes; Monocytes, absol.; Lymphocytes/Leukocytes; Lymphocytes, absol.				
Coagulation	Activated Partial Thromboplastin Time Prothrombin time – INR (International Normalization Ratio)	X X	-- --	X X	X X
Enzymes	AST [Aspartate transaminase] /GOT, SGOT ALT [Alanine transaminase] /GPT, SGPT Alkaline Phosphatase Gamma-Glutamyl Transferase Creatine Kinase [CK] Creatine Kinase Isoenzyme MB [only if CK is elevated] Lactic Dehydrogenase Lipase Amylase	X X X X X X X X X	-- -- -- -- -- -- -- -- --	X X -- X -- -- X X	X X X X X X X X X
Hormones	Thyroid Stimulating Hormone	X	--	--	--

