7.8.3 Vital signs

The analysis of vital signs will be descriptive in nature. Descriptive statistics of vital signs over time and for the difference from baseline (see [Section 6.7](#)) will be provided.

Unscheduled measurements of vital signs will be assigned to planned time points in the same way as described above for laboratory data. However, for vital signs, descriptive statistics will be calculated by planned time point based on the last value of the subject at that planned time point (or assigned to that planned time point).

Clinically relevant findings in vital signs data will be reported as baseline conditions (at screening) or as AEs (during the trial) if judged clinically relevant by the investigator, and will be analysed as such.

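### Unscheduled laboratory and vital-sign values taken after dosing can be summarised in the pre-dose row of the by-time tables

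*SAP*

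**What the plan says.** SAP 7.8.2 treats every unscheduled laboratory value as a repeat of the latest scheduled one, so that "unscheduled measurements will be assigned to the planned time point of the previous scheduled measurement". It continues: "Descriptive statistics will be calculated by planned time point based on the worst value of the subject at that planned time point", which includes values assigned to that time point. SAP 7.8.3 assigns unscheduled vital signs in the same way, but its by-time statistics are "based on the last value of the subject at that planned time point". Both sections also summarise differences from baseline.

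Four other places bear on this:

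- **Protocol 7.3.3** assigns measurements to treatment by their planned time and leaves the detail to the SAP: "These assignments including the corresponding time intervals will be defined in detail in the TSAP".
- **SAP Table 6.1: 1** separates screening from on-treatment at the actual time of dosing, for laboratory data and vital signs as well as adverse events.
- **SAP 6.7** defines baseline as the last non-missing value before dosing.
- **Protocol Table 5.2.3: 1** gives the schedule. Set C, which includes AST, ALT and total bilirubin, reads "Parameters to be determined at Visit 2 on Days 1 (PTM -2:00), 8, 15 and 35". Set B, at 2, 4, 12 and 24 h, is haematocrit only.

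**The concern.** The assignment rule does not stop at the dose. When the previous scheduled measurement is the one at -2:00 on Day 1, a value measured after dosing is filed under a pre-dose time point. The summary rules then favour it: for laboratory data it replaces the true pre-dose value whenever it is worse, and for vital signs it replaces it always, because it is later. It appears in no post-dose row. A post-dose change would be displayed as a pre-dose level, which is the wrong direction for a safety table.

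The protocol foresees such values. Section 5.2.3 provides for retests: "Overnight fasting is not required at the discretion of the investigator or designee for retests". Section 5.2.2.1 says that, when there are clinical symptoms of hepatic injury without laboratory results, "the Investigator should make sure that these parameters are analysed, if necessary in an unscheduled blood test". A test of that kind answers a new event and does not repeat the -2:00 sample.

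**Working it through.** **Step 1: which text governs the row.** The relevant rules, side by side:

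- SAP 7.8.2 and 7.8.3 set the planned time point, and hence the table row, with no condition on dosing.
- Table 6.1: 1 sets the analysis phase by actual time. It does not change the planned time point, and neither 7.8.2 nor 7.8.3 says that the by-time rows follow it. The same value can be on-treatment by phase and pre-dose by row.
- SAP 6.7 protects baseline only. The pre-dose row can then disagree with baseline and show a non-zero difference caused by a post-dose value.
- Protocol 7.3.3 works by planned time, so it does not block the carry-back.

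**Step 2: the exposed window**, meaning the time after dosing during which the previous scheduled measurement is still the pre-dose one:

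| Data | Pre-dose | Next scheduled | Window after dosing |
|---|---|---|---|
| Set C laboratory parameters not in set B, rule read per parameter | -2:00 | Day 8 (168 h) | 0-168 h |
| Laboratory, any safety-laboratory draw counts | -2:00 | 2 h (set B) | 0-2 h |
| Vital signs | -2:00 | 4 h | about 0-4 h |

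The SAP does not say which laboratory reading applies. The vital-signs times come from a flow chart that is damaged in the available text, so the 4 h is approximate.

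**Step 3: size of the effect.** The plan gives no figure to reproduce. Assume one of n subjects has an unscheduled post-dose value that exceeds his pre-dose value by d, that his pre-dose value lies at the group mean, and that the true pre-dose SD is s.

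- Shift in the pre-dose mean, and in the mean pre-dose difference from baseline: d/n.
- New variance: [(n-1)s² + d²(1 - 1/n)]/(n-1) = s² + d²/n.

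| n | d | Mean shift | SD in pre-dose row |
|---|---|---|---|
| 6 | 1 s | 1/6 = 0.17 s | √(1 + 1/6) = 1.08 s |
| 6 | 5 s | 5/6 = 0.83 s | √(1 + 25/6) = 2.27 s |
| 8 | 1 s | 1/8 = 0.13 s | √(1 + 1/8) = 1.06 s |
| 8 | 5 s | 5/8 = 0.63 s | √(1 + 25/8) = 2.03 s |

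n = 6 is the planned number and n = 8 the maximum in Protocol 3.3. The range of d is an assumption.

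A plain-unit example, also assumed: six laboratory values of 25, one of them replaced by 75, give a pre-dose mean of (5 × 25 + 75)/6 = 33.3 instead of 25.0. Six systolic pressures of 120, one replaced by 95, give (5 × 120 + 95)/6 = 115.8 instead of 120.0. The post-dose rows do not move in either case.

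**The case against.** The strongest reply has four parts.

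1. **Phases.** Table 6.1: 1 already divides laboratory data and vital signs at the actual time of dosing. Read together with 7.8.2, it could be taken to allow carry-back only within a phase. That is a sensible reading, but it is not written. The table defines phases, while the by-time statistics are defined by planned time point.
2. **Repeats.** The rule rests on the premise that unscheduled values are repeats, and a retest of the -2:00 sample drawn after dosing fits that premise. It still measures the subject after dosing, and the symptom-driven hepatic test does not fit the premise at all.
3. **Sponsor standards and data review.** SAP 7.8.2 cites a sponsor standard for laboratory data, Protocol 7.3.3 refers to sponsor standards for safety analyses in general, and the report planning meeting reviews discrepant values. The standards cannot be seen here and might contain an exception. SAP 7.8.3 itself cites no standard for vital signs, and SAP 6.2 gives the meeting no rule for these values.
4. **Size.** The 168 h window depends on the per-parameter reading, and d is assumed. Both are true; on the other reading the laboratory window is 2 h.

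What stands is a limit on importance. Clinically relevant findings are still reported as adverse events, a hepatic case meeting the definition is tabulated as an event of special interest, individual values are listed, and the trial is descriptive with PK primary endpoints.

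**Conclusion.** The point holds and is minor. As written, the rule puts a post-dose unscheduled value into the pre-dose row and leaves it out of the post-dose rows; no visible text overrides this. It affects only the by-time descriptive statistics and their differences from baseline, and only if an unscheduled value falls in the window; for laboratory data it must also be the worst value. With 6 to 8 subjects a single misplaced value can visibly move a row. Confidence is medium, because the sponsor's laboratory standard may already contain the exception and the flow chart is damaged.

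**What to change.** Add to SAP 7.8.2 and 7.8.3 that an unscheduled value taken after drug administration is never assigned to a pre-dose planned time point. Show it as a separate post-dose unscheduled entry or list it by actual time, in line with the dosing split in Table 6.1: 1.

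As a secondary clarification, state that the previous scheduled measurement is identified per parameter. Otherwise an unscheduled AST value could be filed under a time point at which only haematocrit was planned.

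Reassignments that do not cross the dose, such as a Day 9 confirmation of a Day 8 sample, can stay as they are. If the sponsor's laboratory standard already covers the case, a one-line reference to that rule is enough for the laboratory part.

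The cost is one or two sentences and minor programming, with no new data.
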